### **Insertion Site Bleeding – Relatedness Category**

1. Where is the location of the bleeding?
  - If in the same location as the sensor, then Probably Related
  - If in a location where a sensor was within 2 days, then Possibly Related
  - If in a location where a sensor was 2+ days in the past, then Probably Not Related
  - If in a location where a sensor was never placed, then Not Related

### **Insertion Site Infection – Severity Category**

1. Do you notice signs of infection that include inflammation, drainage, pus discharge and pain?
  - a. If no, then stop
  - b. If yes, on a scale of 1 to 10, where 1 is very little and 10 is severe, how much inflammation, drainage, pus discharge and pain do you have?
    - If 1 – 8, **Moderate AE**
    - If 9 – 10, **Severe AE**

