- None of the expected device-related adverse events as defined in the protocol and associated documents would be life-threatening or would result in any permanent impairment of a body function or permanent damage to a body structure;
- There are no expected electrical safety risks as the device has passed the electrical safety tests as per EN45502-1 and EN60601;
- If the subject feels any discomfort during the course of the study, he/she will be able to remove the device immediately (the device is not permanent);
- The device is being used to complement, not replace, self-monitoring of blood glucose meter information, and readings are not intended to be used alone to make diabetes self-management decisions. As with the currently approved device and per intended use of similar technologies, subjects in the study will be instructed not to use the device for diabetes therapy or management;

- Subjects will be instructed to monitor their blood glucose levels as per their usual practice.

Adverse events (AE) associated with the use of the device include pruritus (severe itchiness present 48 hours after removal), erythema (reddening of the skin present 48 hours after removal), and inflammation (swelling and pain, defined as 8 or greater on a 10 point scale 48 hours after removal) where the adhesive touches the skin; local infection at insertion site; and shooting pain located at the site of the sensor (defined as 8 or greater on a 10 point scale). Rarely, the sensor wire will fracture when the sensor is being inserted, worn, or removed. If a sensor breaks and no portion of it is visible above the skin, the participant will be instructed to not remove it and seek medical care from the study doctor and/or his staff.

No serious adverse events (SAE) or Unanticipated Problems (UP) are expected as a result of participation in this minimal risk study. However, AE, SAE and UP will be monitored in the following ways:

- Participants in the study will be instructed to call the study doctor's clinical research coordinator to report all AE, SAE and UP related to the use of the CGM devices. The study doctor and/or his staff will assess the severity of any health problems associated with the device, and if needed, see the patient at the study clinic to assure appropriate care.

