- Study coaches will listen for any reports of AE or SAE or UP in the course of their communications with participants, and will connect reporting patients with the study doctor's clinical research coordinator so events can be assessed and documented and patients can receive care, if needed.
- Any reports of AE or SAE or UP received by Dexcom's Technical Support representatives will be documented and reported to the Sponsor. Coaches will then promptly notify the study doctor's clinical research coordinator of these reports so that the coordinator can then follow up with the patient to assess event severity and relatedness, and schedule the patient for care, if needed.

The Sponsor-Investigator will receive CGM-related AE and SAE and UP information from Dexcom through secure data transfers. AE and SAE and UP information from the study doctor will also be stored and transferred securely. Any other records pertaining to AE and SAE from patient conversations with program staff will be recorded and documented using call-management software and the patient's Case Report Form.

The Sponsor-Investigator will ensure proper reporting of AE and SAE and UP to Chesapeake IRB, the CGM manufacturer, the FDA, and any other regulatory bodies according to regulations and standard operating procedures. (See Appendix C for a chart illustrating the reporting process, and Appendix B for AE assessment guidance for coaches.)

Patients will be provided with a summary printout of their recorded CGM data at the end of their participation with CGM. Patients can request a summary printout anytime during the trial. Patients can share their CGM data with their providers.

The Standard of Care guidelines associated with the program direct patients to seek medical care when needed. Guidance exists within the guidelines to seek medical advice when glucose values are extremely high over long periods of time, fluctuate rapidly from high levels to low levels and vice versa, or a

pattern of low glucose values is present. Coaches will remind patients of these guidelines but will not give medical advice. Coaches can send summary CGM data to patients upon patient request.

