### Risks of CGM

When the wire-like sensor is deployed by the applicator, participants can expect a sensation similar to a needle insertion for a blood draw. Risks of CGM use include discomfort during sensor insertion, along with pain, inflammation, redness, swelling, minor bleeding and minor infection at the sensor insertion site. Participants might also experience these symptoms as a result of contact between the adhesive pad of the sensor and the skin. In rare cases, an infection can spread to other parts of the body.

Allergic reactions can develop in response to the sensor, the adhesive, and other parts of the CGM. If these symptoms occur, participants have the ability to remove the CGM at will and can anticipate that their symptoms will clear up within one week.

The sensor and/or applicator may fracture during use. If a sensor remains in the skin, there is minimal risk to the patient as long as a physician confirms there are no symptoms of infection or inflammation.

Patients will be advised that the investigational sensor, transmitter, and smartphone must be removed before Magnetic Resonance Imaging (MRI), Computed Tomography (CT) scan, or diathermy treatment. The device is MR Unsafe. Participants should not bring any portion of the device into the MRI environment. The Dexcom IUO CGM System has not been tested during MRI or CT scans or with diathermy treatment. The magnetic fields and heat could damage the device, causing it to stop displaying glucose readings, display inaccurate glucose readings, or prevent alerts.

Patients will also be advised of CGM system warnings that may affect the proper operation of the device and/or the patient's safety. These warnings will be described in the informed consent and authorization form, and in the informational materials provided to patients when they receive their systems.

Patients will be provided with a phone number for Dexcom's Technical Support. Staff for this line will be well-qualified to address any potential questions and risks associated with the investigational device. Significant or serious health risks with CGM are not anticipated.

The same precautions have been taken to code and/or encrypt the investigational system's electronic data as have been taken with the commercial Dexcom devices. Regardless, throughout the program, patients will be advised not to rely on the device to make any treatment decisions, and to measure their blood glucose in order to confirm any symptoms of hypoglycemia.

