### **Insertion Site Bruising – Severity Category**

1. On a scale of 1 to 10, where 1 is very little, and 10 is severe, how much bruising do you have?
  - If 1-5, do not record as AE, **unless the bruise is getting bigger, see question 2**
  - If 6-7, Mild AE
  - If 8-9, Moderate AE
  - If 10, Severe AE
2. Is the bruise or bump getting bigger?
  - If no, stop
  - If yes, **Moderate AE**
  - If yes and bruise is significantly getting bigger, **Severe AE**

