### **Insertion Site Bruising – Relatedness Category**

1. Where is the location of the pain or discomfort?
  - If in the same location as the sensor on your skin, then Probably Related
  - If in a location where a sensor was within 2 days, then Possibly Related
  - If in a location where a sensor was 2+ days in the past, then Probably Not Related
  - If in a location where a sensor was never placed, then Not Related

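### Appendix B's bruising and infection question sets can grade or attribute the same device event in different ways

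*Combined protocol and SAP*

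**What the plan says.** Under the introduction to Appendix B, a coach matches a participant's complaint to a guidebook. The coach then uses set questions to assign a severity (Mild, Moderate, Severe) and a relatedness category, and documents the answers.

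- **Bruising, relatedness.** The question is "Where is the location of the pain or discomfort". The four answer options depend on whether a sensor is there now, was there within two days, was there longer ago, or was never there.
- **Bruising, severity.** Question 1 grades a 1-10 rating: 1-5 is not recorded, 6-7 is Mild, 8-9 Moderate, 10 Severe. The 1-5 line alone carries an exception, "unless the bruise is getting bigger, see question 2". Question 2 asks "Is the bruise or bump getting bigger": yes is Moderate, and growing significantly is Severe.
- **Infection, severity.** The opening question is "Do you notice signs of infection that include inflammation, drainage, pus discharge and pain". The first branch is "If no, then stop". A yes leads to one 1-10 score covering all the signs together: 1-8 is Moderate, 9-10 Severe.
- **Section 9 (Assessment of Safety)** lists "local infection at insertion site" among device adverse events and sets no condition on the number of signs.

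**The concern.** Bruising and infection at the sensor site are effects the protocol prepares for with an investigational sensor. With 500 participants, 10 weeks of wear and 10-day sensors, full use would mean 70 / 10 = 7 sensors each, or up to 500 x 7 = 3,500 insertions. Coaches put these questions to participants by phone, and the resulting severity category determines whether the call is transferred to the study doctor's staff. If the questions point to the wrong site, give two grades for one bruise, or leave the threshold for infection open, two coaches can code the same event differently. Section 9 commits the sponsor to reporting these events to the IRB, the manufacturer and the FDA.

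**Working it through.** The plan gives no figure to reproduce here. The check compares the question sets and counts their branches. The counts are branches, not event rates.

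**1. Bruising relatedness.** Appendix B has eight relatedness steps: redness or rash, itchiness, pain or discomfort, swelling, bruising, bleeding, infection and broken sensor wire. Seven ask about their own complaint. Bruising alone asks about another one, in the same words as the pain step. Two cases follow:

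- A painless bruise: the question has no literal answer.
- A bruise under the current sensor with discomfort where no sensor was ever placed: the literal answer is Not Related, whereas the bruise's own location gives Probably Related.

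**2. Bruising severity.** Inputs: 10 ratings x 3 growth states (none, growing, significantly growing) = 30 combinations.

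*Reading A: question 2 is asked of everyone, and its last line overrides the one before.* For ratings 1-5, question 1 gives no grade and defers to question 2, so there is no conflict. Two grades arise only for ratings 6-10 with growth: 5 x 2 = 10 combinations.

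| Rating | Question 1 | Growing (question 2: Moderate) | Significantly growing (question 2: Severe) |
|---|---|---|---|
| 6 | Mild | conflict | conflict |
| 7 | Mild | conflict | conflict |
| 8 | Moderate | agree | conflict |
| 9 | Moderate | agree | conflict |
| 10 | Severe | conflict | agree |

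Three of the 10 agree, so 10 - 3 = 7 of 30 carry two different grades. If a significantly growing bruise is instead taken to trigger both lines of question 2, all 10 significantly growing combinations have two grades. Adding the three growing ones (ratings 6, 7 and 10) gives 13 of 30.

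*Reading B: question 2 is asked only for ratings 1-5, where the cross-reference stands.* With the last line overriding, 0 of 30 conflict, but the order of grades inverts:

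- Growing: rating 3 is Moderate, rating 7 is Mild.
- Significantly growing: rating 3 is Severe, rating 9 is Moderate.

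**3. Infection.** Four signs, each present or absent, give 2^4 - 1 = 15 combinations with at least one sign.

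- All four required: 1 combination proceeds and 15 - 1 = 14 stop ungraded.
- Any one sufficient: 15 proceed and 0 stop.

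The wording does not settle which reading applies.

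**The case against.** The strongest reply is that the infection wording introduces its signs as things included, which reads naturally as a list of examples. A participant who has just reported pus is unlikely to be turned away for lack of pain. Nor does stopping mean discarding. Where Appendix B wants no record it says so expressly, as for low swelling ratings, and in the second questions on redness and bruising a stop merely ends the questioning. Other routes exist too. Section 9 tells participants to call the study doctor's coordinator and says "Study coaches will listen for any reports of AE or SAE or UP in the course of their communications with participants", with referral for assessment and documentation. Section 6 (Integration with patient care) has the coordinator assess severity and relatedness.

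Much of this stands. A reader might infer that infections go unrecorded; the documents support only a risk that these questions end without a grade. A reader might also put a percentage on missed infections by assuming how often each sign occurs and multiplying. The documents give no such frequencies, and signs of one infection tend to occur together, so that product would not be a sound estimate. Nor can one say that adverse event tables would be wrong, since Section 10 describes none. The absence of a question on spread, which Section 12 mentions ("In rare cases, an infection can spread to other parts of the body"), is not a contradiction: Section 12 calls it rare, and any yes is already at least Moderate.

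The reply does not remove the ambiguity. Drainage and pus have no other question set, and swelling rated 1-5 is not recorded, so the neighbouring sets are only a partial backstop. A call that stops also yields no severity category to prompt a transfer. The red highlighting that marks which categories trigger transfer is lost in the text, so nothing can be said about which grades would bypass medical review.

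On bruising, a coach may look past the wording, since the heading and answer options make the intent plain, and pain will often be at the bruise. That limits the harm but leaves the question wrong. Confining question 2 to ratings 1-5 removes the double grades only by producing the inversion shown above.

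**Conclusion.** The point holds as one about consistent grading and attribution, not about lost events. The bruising relatedness question names the wrong complaint; this matters mainly when a bruise is painless or the pain is elsewhere. The bruising severity step fails on either reading: 7 of 30 combinations with two grades (13 of 30 if both growth lines apply), or a higher grade for a growing bruise rated 3 than for one rated 7. The infection step is ambiguous, with 14 of 15 or 0 of 15 sign combinations ending ungraded according to the reading. Section 9 does not define infection, so there is no direct contradiction, but the two places should be reconciled. How many participants would be affected cannot be derived from the documents. No hypothesis test or sample size is touched, because the study has neither. The correction is worth making because these answers set the severity and relatedness of device events for an investigational sensor.

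**What to change.** 1. In the bruising relatedness step, ask for the location of the *bruising*.
2. In the bruising severity step, ask question 2 at every rating and state one precedence rule, for example that the higher of the two grades is recorded. The study doctor should confirm the rule.
3. In the infection step, ask whether *any of the following* signs is present, or ask each sign separately. Reconcile the threshold with the unconditional listing in Section 9, and have the study doctor confirm how the answers map to grades.

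The cost is rewording two coach question sets and briefing the coaches. Slightly more infections may be recorded.

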### **Insertion Site Infection – Relatedness Category**

1. Where is the location of the infection?
  - If in the same location as the sensor on your skin, then Probably Related
  - If in a location where a sensor was within 2 days, then Possibly Related
  - If in a location where a sensor was 2+ days in the past, then Probably Not Related
  - If in a location where a sensor was never placed, then Not Related

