## 23. Appendix B

### Adverse Events Severity and Relatedness Questions

May 2017

When patients share a complaint, program coaches will identify the complaint in the Anticipated Complaints Guidebook. Based on the complaint type, coaches will then ask questions to determine:

1. Severity of the complaint (e.g., Mild, Moderate, or Severe), and
2. Relatedness of the complaint to the use of program devices (e.g., Not Related, Probably Not Related, Possibly Related, and Probably Related)

Coaches will document answers in the templates provided, including the Adverse Event document.

If the complaint falls in any of the severity categories highlighted in red, the coach will make a “warm transfer” to the study doctor and/or his staff so that the patient can be scheduled for an ancillary appointment.

If the complaint is an emergency, patients will be instructed to call 911.

If a patient has a complaint that is not listed in the Anticipated Complaints Guidebook, the coach can “warm transfer” the patient to the study clinic for guidance. The coach will document as much as possible in Adverse Event document. Follow up with the clinic will determine severity and relatedness.

Coaches will contact the PI when situations arise that are not covered in the Anticipated Complaints Guidebook.

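### Appendix B's location-only rule codes a rash, and possibly an infection, found only where no sensor was ever placed as Not Related, although Section 12 lists allergic reactions and spreading infection as CGM risks

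*Combined protocol and SAP*

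**What the plan says.** Appendix B has coaches match a complaint to the Anticipated Complaints Guidebook and then ask set questions about its severity and the "Relatedness of the complaint to the use of program devices". For Skin Redness or Rash and for Insertion Site Infection, the relatedness part is a single question about where the complaint is. It has four answers:

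- At the current sensor site: Probably Related.
- At a recent site: "If in a location where a sensor was within 2 days, then Possibly Related".
- At an older site: "If in a location where a sensor was 2+ days in the past, then Probably Not Related".
- Elsewhere: "If in a location where a sensor was never placed, then Not Related".

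Section 12, Risks of CGM, says of infection: "In rare cases, an infection can spread to other parts of the body". It says of allergy: "Allergic reactions can develop in response to the sensor, the adhesive, and other parts of the CGM".

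On escalation, the introduction to Appendix B says "If the complaint falls in any of the severity categories highlighted in red, the coach will make a" warm transfer to the study doctor or his staff. For complaints missing from the Guidebook, the coach can transfer the patient to the clinic, and "Follow up with the clinic will determine severity and relatedness". Section 6 (Integration with patient care) gives the study doctor's clinical research coordinator the task of judging severity and relatedness when patients make contact about device-associated health problems. Section 9 has coaches connect patients who report events to the coordinator for assessment and documentation. It also has the coordinator judge severity and relatedness for events passed on by the manufacturer.

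**The concern.** Location is a sensible proxy for a purely local reaction. It fails for a reaction that can appear away from the device, and Section 12 names one that can (infection that spreads) and another for which it gives no location (allergy). Neither script asks whether redness, pain or infection at a sensor site came first, which is the fact that would link a distant finding to the device.

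At stake is the attribution of adverse events for an investigational CGM system that Section 3 describes as not FDA-approved. Section 9 makes the Sponsor-Investigator responsible for reporting events to the IRB, the manufacturer and the FDA. A fixed rule that returns the strongest negative code, without clinical judgement, can put a wrong attribution into that record.

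**Working it through.** No arithmetic applies: the documents give no event rate, and the point is one of logic. The check applies the scripts as written to the reactions in Section 12.

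**Step 1: what code results?**

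| Situation | Code under the script |
|---|---|
| Rash only at a never-used site, arising from an allergic reaction to the CGM | Not Related |
| Infection only at a never-used site, having spread from a sensor site | Not Related, if the infection script is used |
| Rash or infection still at the current sensor site and also elsewhere | No rule for several locations; the sensor site itself gives Probably Related |
| Rash or infection at a former site | Possibly Related (within 2 days) or Probably Not Related (2 or more days) |

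The conflict with Section 12 lies in the first two rows.

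**Step 2: does the script apply?** The rash script is headed Skin Redness or Rash, with no mention of the insertion site, so a distant rash falls within it. The infection script is headed Insertion Site Infection. An infection elsewhere could be forced into it, or handled as an unlisted complaint with relatedness settled through the clinic. The documents do not choose. The first row is therefore firm and the second conditional.

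**Step 3: does a later step correct the code?**

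- Clinic determination of relatedness, as Appendix B states it, is for unlisted complaints. Rash and insertion-site infection both have scripts.
- Transfer depends on severity, not relatedness. In the rash script, a redness score of 6 to 7 is a Mild AE, 8 to 9 Moderate and 10 Severe. In the extracted text only the Moderate and Severe lines carry a mark. If that mark stands for the red highlighting, which is not visible, a mild rash is recorded but not transferred under Appendix B. In the infection script, scores 1 to 8 are Moderate and 9 to 10 Severe, so every infection with signs is at least Moderate and transfer is more likely.
- The coordinator route in Section 6 starts from health problems associated with the CGM, or from a concern that may be study-related. The patient instruction in Section 9 likewise covers events related to the CGM devices. Both entry points presuppose some link to the device, which the script may already have denied.
- For events that coaches hear, Section 9 provides for assessment and documentation by the coordinator. It mentions relatedness explicitly only for manufacturer-reported events.
- No visible sentence says whose relatedness code stands if coach and coordinator differ. The Appendix C reporting chart is not visible either.

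**Result.** The scripts can return a code that contradicts Section 12, and no visible text guarantees its correction. The weakest spot is mild rash.

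**The case against.** The strongest reply is that the coach's code is a first screen. The coordinator assesses relatedness in Section 6, coaches connect reporting patients to the coordinator in Section 9, transfer follows severity whatever the relatedness code, and unlisted complaints go to the clinic. Much of this stands. The severity code is unaffected, and clinical staff will probably see any infection. What remains open is precedence between the two assessments and the handling of complaints below the transfer threshold.

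Several stronger readings are tempting but lack support:

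- A reader might infer that anything away from the present sensor is coded Not Related. Former sites are coded Possibly or Probably Not Related; only never-used sites get the flat negative.
- A reader might infer that a spread infection must be coded Not Related. If the sensor site is still infected, that site gives Probably Related, and the unlisted-complaint route may apply.
- A reader might infer that the device's most serious reactions are removed from the safety result. Section 12 does not rank the reactions, expects symptoms to clear within one week of removing the CGM, and does not anticipate serious risks. Removal is not shown, given the coordinator's role.
- A reader might infer that the non-significant-risk position depends on these codes. Section 9 rests that position on the earlier IRB designation, comparable devices, needle dimensions, electrical testing and manner of use, not on this study's event rate. Section 10 plans no device-related event rate.

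**Conclusion.** The concern holds in a limited form. A rash found only where no sensor was ever placed is coded Not Related by rule, and an infection found only there may be, although Section 12 recognises that the CGM can cause allergic reactions and infections that spread. Such events are at risk of being miscoded as unrelated; the documents do not show that they will be.

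The extent is one branch of four in each of two scripts. The documents call spread of infection rare and give no frequency for allergic reactions, so no expected number of affected events can be derived. The conclusion rests on coaches applying the scripts as written. For mild rash it also rests on the assumption that only the marked severity categories trigger transfer. The original highlighting and the Appendix C chart could settle the transfer threshold and perhaps the precedence question, but would not remove the conflict between the scripts and Section 12.

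**What to change.** Reconcile the rash and infection relatedness scripts in Appendix B with Risks of CGM in Section 12:

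1. In both scripts, replace the automatic Not Related branch with: Undetermined – relatedness assigned by the study doctor's staff.
2. In both scripts, add one question: was there redness, pain or infection at a sensor site before this began?
3. State in Appendix B that the relatedness assessment of the coordinator or study doctor supersedes the coach's code.

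The change uses staff and roles already in the plan and alters no treatment rule. It costs one branch and one question in each of two scripts, one sentence on precedence, and a few more coordinator assessments, some of which will concern rashes that have nothing to do with the device.
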